## Potential pitfalls and contingency plan.

Should we be unable to detect significant changes in temperature in the digits after gammaCore vagal stimulation, we will consider using gammaCore vagal stimulation at different time intervals. Also, to eliminate effects of seasonal variability on RP, we will recruit all subjects for this study in the same season. To avoid effect of environment temperature variability on evaluation of blood flow in the digits, we will perform the testing at standard room temperature (23°C + 0.5°C).

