#### **Abstract**

Raynaud's phenomenon (RP) is a common vascular disorder that affects approximately 10% of the general population. RP is associated with significant morbidity that may include loss of the digits due to repeated episodes of vasospasm of the digital arteries in addition to significant impairment of quality of life. It is well known that cold exposure precipitates episodes of RP, but the mechanism for cold sensitivity is not known, and treatment of RP is not satisfactory to the subjects and their physicians.

Our goal in this proposal is to test the possibility that non invasive vagus nerve stimulation (nVNS) with gammaCore may be an effective and well tolerated therapy for RP. We will perform the first proof of concept human study to demonstrate the clinical efficacy and safety of nVNS using gammaCore in RP.

We anticipate at the conclusion of the proposed work that we will have gained fundamental understanding of the role of nVNS as a potential therapy for RP, a truly unmet medical need. If successful in demonstrating measurable local vasodilatory effects, we will proceed in a second phase of the study to evaluate the effects of gammaCore on RP associated with Scleroderma.

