## The Specific Sequential Aims of this application are as follows:

- Aim 1: Evaluate the clinical efficacy of gammaCore (16 subjects) vs sham device (16 subjects) in preventing vasospasm in 32 PRP subjects.
- Aim 2: Evaluate the clinical efficacy of gammaCore (16 subjects) vs sham device (16 subjects each) on Raynaud's symptoms and chronic PRP in 32 subjects with chronic PRP for four weeks using Raynaud's condition score.
- Aim 3: Observe response rates in an open label fashion after sham subjects are transitioned to gammaCore.

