#### D. APPROACH and METHODOLOGY

# 1. Assessment of digital blood flow in response to cold challenge test

We used FLIR thermography system (Wilsonville, OR) to evaluate blood flow in the digits in response to cold challenge test. The advantage of IT is that we can obtain dynamic assessment of blood flow in the hands as reflected by change in temperature in response to cold challenge tests, as well as the ability to obtain single point measurements. **Figure 2** shows dynamic changes in surrogate marker of blood flow as detected by thermal images during the three phases of active Raynaud's phenomena that we were able to reproduce by cold challenge test.

**Figure 2:** An illustrative example of dynamic changes in vascular perfusion that are detected by infrared thermography. A) Active vasospasm, B) spontaneous improvement in blood flow, C) Hyperemia. Blue-yellow regions indicate areas of lower perfusion compared to red regions.

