## Demonstrating the effect of treatment in response to cold challenge.

We will calculate absolute temperature, DDD, and DDDI from images of both hands taken at baseline, 1 min, 5 min, 10 min, 15 min and 20 minutes after cold challenge at the dorsum and digits 2nd-4th. High gradient of DDDI indicates insignificant response of the treatment modality.

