## Statistical analysis.

Comparisons between absolute temperature, DDD, and DDDI between subjects and visits will be made. Mean values and standard deviations of the measurements IT end points will be determined. Sequentially, the differences in the mean values of temperature after a baseline and in response to cold challenge will be calculated and categorized as greater or less than1.2-fold change from the baseline average. Also, we will measure absolute temperature, DDD, and DDDI across the 2nd-4th digits bilaterally. We will calculate the mean of all absolute temperatures, DDD, and DDDI values and rate of change, and use t-test to calculate P value. P value <0.05 will be considered statistically significant. We will use one-way ANOVA for the means will be used for statistical analysis. Statistical significance will be considered if P < 0.05.

Anticipated results and interpretation. We predict that these experiments will provide the first clinical evidence that nVNS with gammaCore may be an effective treatment in PRP, by demonstrating that the stimulation abrogates vasospasm that is classically induced by cold challenge in subjects with PRP.

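### Aim 1 is gammaCore against sham, but no analysis or decision text requires that contrast, so a change shared by both arms could be read as success

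*Combined protocol and SAP*

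**What the plan says.** The Specific Aims are comparative. Aim 1 reads "Evaluate the clinical efficacy of gammaCore (16 subjects) vs sham device (16 subjects) in preventing vasospasm in 32 PRP subjects". Experimental Design randomizes 1:1, and sham subjects move to gammaCore only after the Week 4 cold challenge. The challenges at Weeks 0 and 4 are therefore sham-controlled and the one at Week 8 is not.

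The contrast is not carried into the text that governs analysis and next steps:

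- **Statistical analysis:** "Comparisons between absolute temperature, DDD, and DDDI between subjects and visits will be made". Temperature changes are to be "categorized as greater or less than1.2-fold change from the baseline average". The investigators will "use t-test to calculate P value" and will also use a one-way ANOVA. Neither test is tied to named groups, and the t-test is not said to be paired or two-sample.
- **Potential pitfalls and contingency plan:** the unsuccessful case is worded "Should we be unable to detect significant changes in temperature in the digits after gammaCore vagal stimulation". Other stimulation intervals would then be considered.
- **Abstract:** "If successful in demonstrating measurable local vasodilatory effects, we will proceed in a second phase of the study", in scleroderma-associated disease. No comparator, measure, visit or threshold is given.

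The Figure 2 legend, describing phases reproduced by cold challenge, lists "B) spontaneous improvement in blood flow, C) Hyperemia" after active vasospasm.

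**The concern.** Half of the randomized subjects receive sham so that a change after gammaCore can be separated from a change that would have occurred anyway. Several such changes are plausible here:

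- a placebo response to a device that the subject applies;
- an effect of repeating the cold challenge;
- regression to the mean, because the Thermography section enrols subjects for exceeding a DDD or DDDI threshold at screening;
- spontaneous rewarming, if the result is read before and after within one session.

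If the result is judged on change in the gammaCore arm alone, all of these count towards success. A second phase could then start when the two arms had behaved identically.

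**Working it through.** **Step 1. What each text requires.**

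| Section | What is compared | Sham named? |
|---|---|---|
| Specific Aims, Aim 1 | gammaCore v sham | Yes, but no test or criterion |
| Statistical analysis | Subjects and visits; change from baseline | No |
| Potential pitfalls and contingency plan | Change after gammaCore | No |
| Abstract, second-phase condition | Not stated | No |

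The one row that names sham sets no criterion, and the rows that describe an analysis or a next step do not name sham. A paired test within the gammaCore arm would comply with the text as written.

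**Step 2. Is there a figure in the plan to reproduce?** None bears on this point. The sample-size statement (90% confidence, 10% margin of error) gives no effect size, SD or power. It is a separate matter, and nothing below depends on it.

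**Step 3. How often identical arms would pass.**

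Inputs from the plan: n = 16 per arm; significance at P<0.05. Assumed: two-sided tests, normally distributed change scores, and a true change of d SD that is the same in both arms. The documents give neither an SD nor an expected sham change, so d is shown as a range.

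*Within gammaCore only* (paired t-test on 16 change scores): df = 15, critical value 2.131, noncentrality d × √16 = 4d. The chance of a significant improvement is P(T > 2.131), where T is noncentral t with 15 df and noncentrality 4d.

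*gammaCore minus sham* (two-sample t-test, 16 v 16): df = 30, noncentrality (d − d) × √(16/2) = 0. The result does not depend on d.

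| Shared change d (SD) | Noncentrality 4d | Within-arm significant improvement | Between-arm significant, two-sided |
|---|---|---|---|
| 0 | 0 | 2.5% | 5% |
| 0.2 | 0.8 | 11% | 5% |
| 0.3 | 1.2 | 20% | 5% |
| 0.5 | 2.0 | 46% | 5% |
| 0.8 | 3.2 | 85% | 5% |
| 1.0 | 4.0 | 96% | 5% |

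The within-arm column counts improvement only. The like-for-like between-arm figure, a difference favouring gammaCore, is 2.5%. A simulation of 100,000 trials per row agreed: at d = 0.5, 46.7% within-arm and 4.9% between-arm, two-sided.

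**Step 4. Cost of the between-arm criterion.** With a true difference of δ SD, the noncentrality is δ × √8 on 30 df. Power reaches 80% at δ = 1.02 and 90% at δ = 1.19.

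**Step 5. Why one measure at one visit.** If either of two measures at either of two visits could carry the result, the chance of at least one false positive would be 1 − 0.95⁴ = 18.5% for independent tests. Correlated tests would give less, but still more than 5%.

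**The case against.** The strongest reply is that the comparison with sham is plainly intended. Aims 1 and 2 both set gammaCore against sham, the trial is randomized, and the control is kept through the Week 4 challenge. Success in the Abstract can fairly be read as success on those aims. This stands as a statement of intent, but it does not supply the missing instruction, because the aims set no criterion and the analysis text names no arms.

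A reader might infer more than the documents support:

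- *That the plan has a formal decision rule that ignores sham.* It does not. The contingency text only says that other stimulation intervals will be considered, and it neither declares failure nor blocks anything. The Abstract is silent on the comparator; it permits a within-arm reading without requiring one.
- *That response is to be judged from DDDI without sham.* The sentence "High gradient of DDDI indicates insignificant response of the treatment modality" gives the direction in which DDDI is read. It sets no success rule and does not exclude a comparison with sham.
- *That spontaneous rewarming alone would yield success.* Figure 2 is an illustrative example, and images are taken at fixed minutes after the challenge. If visits are compared at the same minute, rewarming occurs at both and largely cancels. It matters only under a pre/post reading within a session, which the plan neither specifies nor rules out. Placebo response, repeat testing and regression to the mean do not cancel in this way.

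It is also fair to say that the percentages are general properties of a t-test on 16 subjects with an assumed d. They show what the text allows and do not predict what the investigators will do.

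**Conclusion.** The point holds in limited form. The plan states a comparative aim, but nothing in its analysis text, its description of a negative result or its condition for a second phase requires the comparison. This is more than missing detail, because the one explicit wording, change after gammaCore, gives the wrong answer whenever both arms change alike: about 20%, 46% and 85% false success at a shared change of 0.3, 0.5 and 0.8 SD, against 5% for the between-arm test. At a shared change of zero there is no inflation.

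These figures rest on two-sided tests, normal change scores, 16 evaluable subjects per arm and values of d that the documents do not give. The randomized data will support the right analysis, so the defect can be repaired in the text and should be repaired before data are examined.

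**What to change.** 1. **Statistical analysis.** State that the test for Aim 1 is the gammaCore-minus-sham difference, reported with its confidence interval, on one pre-named thermography measure at one pre-named sham-controlled challenge (for example Week 4). Say that the t-test is a two-sample comparison of the randomized arms, and give its direction and threshold. Label other measures, the Week 0 challenge, the open-label Week 8 challenge and all within-arm changes as supportive or descriptive.
2. **Potential pitfalls and contingency plan.** Replace the reference to change after gammaCore with failure to show that same gammaCore-minus-sham difference.
3. **Abstract.** Make the second phase conditional on that same difference.

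The section on demonstrating the effect of treatment in response to cold challenge needs no change.

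The cost is three wording changes and no new data. The criterion becomes harder to meet: with 16 per arm, a true difference well below about 1 SD will often be missed. That is a reason to report the confidence interval and to interpret a non-significant result cautiously. It is not a reason to fall back on within-arm change.

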# Thermography

We will use FLIR system to measure temperature and blood flow at the digits. After the cold challenge, subjects will place their hands on a setup of a carpet square measuring a length of 42.5 cm by 29.5 cm wide, placed backing side up (to reduce reflection), on a table with a grate resting on the carpet where the subject will be instructed to rest hands on. We will use 2 thresholds for use as screening when subjects do the first cold challenge without neurostimulation:

- 1. A Distal Dorsal Difference (DDD) >1°C at base line or
- 2. DDDI should > 20% at 5 min after the cold stress.

Subjects who meet the screening threshold of clinically meaningful change from baseline on the initial cold challenge will be enrolled into the study.

Week -4 (Screening). The screening visit where eligibility testing will be performed utilizing the cold challenge test, a baseline image will be taken, and physician verbal history interview performed. Subjects will begin to keep a diary of Raynaud's symptoms and number of attacks. Throughout the study, the diary will be collected at week 0, 4, 8, and 12. A diary will be provided at week -4, 0, 4, and 8. Beginning at week 0, stimulation time and occurrences with gammaCore device will be recorded in the diary along with at week 4. There is no use of gammaCore or sham at this point. Subjects continue their current standard of care treatments, except for medications prohibited while enrolled in the study.

Week 0 (Randomization). The first 32 subjects that meet screening criteria will be enrolled into the study. Diaries from Week -4 to Week 0 will be collected, and a new diary given. The 32 subjects will be randomized 1:1 to either sham device (16) or gammaCore device (16). At week 0 subjects will have a follow up image #1 taken and then be treated with sham or gammaCore -20 minutes prior to cold challenge. The first set of stimulation begins at -20 minutes (2 minutes on each side of the neck for a total of 4 minutes) and then at -4 minutes the second set of stimulation occurs (2 minutes on each side of the neck for a total of 4 minutes)

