Week 8. Subjects return for cold challenge test and bring device back with them to be returned. The diary from week 4 to 8 will be collected and subjects will be provided a new diary to record their Raynaud's symptoms and number of attacks in. Subjects will have follow up image #3 taken and then will be treated with gammaCore -20 minutes prior to cold challenge (stimulation 2 minutes each side of the neck for a total of 4 minutes) and then at time -4 (stimulation 2 minutes each side of the neck for a total of 4 minutes, performed by the subject and monitored by the investigator, or delegated study personnel) immediately before cold challenge. Using FLIR thermography absolute temperature, DDD, DDDI will be calculated from images of both hands taken at baseline, obtained by a video where images are captured at 1 min, 5 min, 10 min, 15 min and 20 minutes after cold challenge will be measured at the dorsum and digits 2nd-4th. Images measuring the absolute temperature, DDD, and DDDI at specific regions as well as the average of all regions will be generated as a surrogate

marker of blood flow. Study will end at Week 12 with the possibility of long term open label extension that will be decided later.

Week 12. Subjects will return to turn in completed diary.

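### Same-season recruitment limits but cannot eliminate seasonal effects over a 16-week follow-up, so between-visit and open-label changes can be confounded with season

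*Combined protocol and SAP*

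**What the plan says.** Under Potential pitfalls and contingency plan, the protocol states the purpose and the remedy together: "to eliminate effects of seasonal variability on RP, we will recruit all subjects for this study in the same season". It names neither the season nor the length of the recruitment window. The next sentence treats room temperature as a separate problem and fixes testing at 23°C with a 0.5°C tolerance.

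The visit schedule is under Thermography. Participation starts at Week -4: "The screening visit where eligibility testing will be performed utilizing the cold challenge test", and the diary begins then. It ends eight weeks after the switch to open label: "Study will end at Week 12 with the possibility of long term open label extension that will be decided later". Over that time, "the diary will be collected at week 0, 4, 8, and 12". Cold challenges are at Weeks -4, 0, 4 and 8. The last one is described as follows: "Week 8. Subjects return for cold challenge test and bring device back with them to be returned". The final visit has no thermography: "Week 12. Subjects will return to turn in completed diary".

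The Statistical analysis section says: "Comparisons between absolute temperature, DDD, and DDDI between subjects and visits will be made". It names a t-test and one-way ANOVA with P<0.05, and includes no term for date, season or outdoor temperature. It does not describe a diary analysis.

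Under Specific Aims, Aims 1 and 2 compare gammaCore with sham (16 per arm). Aim 3 observes response after sham subjects move to gammaCore. All subjects are on open-label active treatment once the Week 4 cold challenge is done.

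**The concern.** The plan itself accepts that season affects Raynaud's phenomenon and names cold exposure as the trigger. It then claims to have removed the effect with a rule on enrolment dates alone. Such a rule makes subjects more alike at a given visit. It does nothing to stop the weather changing between one subject's visits. It also means that nearly everyone reaches a given visit at about the same time of year, so a visit effect and a season effect become hard to tell apart.

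At stake is the reading of any change over time. A shift towards warmer weather would look like benefit, and a shift towards colder weather would hide it. If the claim of elimination stands, a significant before-after difference could be credited to the device with no caveat.

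**Working it through.** The plan gives no figure to reproduce here, so the check is timeline arithmetic followed by a look at which comparisons are exposed.

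**1. Length of follow-up.** 12 - (-4) = 16 weeks per subject. The last cold challenge is 8 - (-4) = 12 weeks after screening. If a season lasts 13 weeks (assumed), nobody can complete all of the study within one season, however tight the recruitment.

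**2. Share of visits outside the recruitment season.** Let L = 13 be the season length, w the recruitment window in weeks (entry uniform over it, starting at season start), and lag the time from the recruitment date to the visit. The share is (w - (L - lag))/w, bounded between 0 and 1. For w = 0 it is 1 if lag > L and 0 otherwise. Examples, counted from screening: Week 4 with w = 13 gives (13 - 5)/13 = 62%; Week 8 with w = 4 gives (4 - 1)/4 = 75%.

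| Recruitment window, and date counted from | Wk 0 | Wk 4 | Wk 8 | Wk 12 | Mean, Wk 0-12 | Mean, Wk 4-12 | Cold challenges, Wk 0-8 |
|---|---|---|---|---|---|---|---|
| 13 weeks, screening | 31% | 62% | 92% | 100% | 71% | 85% | 62% |
| 13 weeks, randomisation | 0% | 31% | 62% | 92% | 46% | 62% | 31% |
| 4 weeks, screening | 0% | 0% | 75% | 100% | 44% | 58% | 25% |
| All at season start, screening | 0% | 0% | 0% | 100% | 25% | 33% | 0% |

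If all subjects were randomised on the first day of the season, every visit from Week 0 on would fall inside it, but screening and the Week -4 to 0 diary would fall before it. If a season is taken as a 26-week half-year with entry spread over all of it, the shares at Weeks 0, 4, 8 and 12 are 15%, 31%, 46% and 62%, counted from screening. With a 13-week window in such a half-year, only Week 12 is affected (23%).

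**3. Visit number tracks calendar time.** Measure time from the start of recruitment. With w = 4, screening visits occupy weeks 0 to 4 and Week 8 visits occupy weeks 12 to 16, so they never overlap. With w = 13 the ranges are 0 to 13 and 12 to 25, which overlap by one week. The data would hold little or no information for separating a visit effect from a season effect.

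**4. Which comparisons are exposed.** Write τ for the device effect and δ for a seasonal shift common to both arms.
- gammaCore minus sham at the same visit, to Week 4: (τ + δ) - δ = τ. The shift cancels.
- Change between visits within an arm: the gammaCore arm estimates τ + δ and the sham arm estimates δ plus any sham response.
- Former sham subjects, Week 4 to Week 8 (Aim 3): τ + δ, with no concurrent sham group from which to learn δ.
- Diary for Weeks 8 to 12: the device is handed back at Week 8, so this change mixes season with the end of device use.

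**5. Illustration only.** Suppose a paired t-test in 16 subjects, no device effect, correlation r between visits and a drift of d SD. The noncentrality is d√16/√(2(1 - r)). At d = 0.25 it is 1.00 (r = 0.5) or 1.29 (r = 0.7), giving false-positive rates of 15.5% and 22.7%. At d = 0.5 the rates are 46.5% and 67.5%. An unpaired t-test on the same data gives about 2-4% at d = 0.25 and 17-21% at d = 0.5. The drift sizes and correlations are assumed, and the plan does not say whether its t-test is paired.

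**The case against.** The strongest reply is that the efficacy aims do not depend on the claim. Aims 1 and 2 are randomised, concurrent comparisons up to Week 4, and Aim 3 only says it will observe. The between-visit comparisons that the Statistical analysis section names are of thermography, done at 23°C after 20 minutes' acclimatisation in a single layer of clothing, with water held at 15°C ± 0.5°C. Same-season entry also serves a legitimate purpose, since it reduces seasonal differences between subjects.

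All of this stands, and it narrows the point. It does not dispose of it. The room controls cannot reach attacks and symptoms recorded at home, and they do not rule out a seasonal change in vascular reactivity. The Statistical analysis section sets P<0.05 without reserving it for the concurrent contrast.

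A reader might also infer more than the documents support:
- **That most later visits fall in another season.** This depends on a season length and recruitment window that the plan does not state. The table shows it true in some cases and false in others.
- **That the drift would look like improvement.** No season is named, so the direction is unknown.
- **That the false-positive rate is inflated by a known amount.** The larger figures need a paired test and an assumed drift. The unpaired test, equally consistent with the text, shows no excess over 5% at 0.25 SD.
- **That the gammaCore-versus-sham result is biased.** A shift common to both arms cancels.

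**Conclusion.** The concern holds in limited form. The plan claims a property that its design does not have: fixing enrolment dates cannot eliminate seasonal effects over 16 weeks. Some of each subject's participation falls outside a 13-week season. The share of Week 0 to 12 visits affected runs from 25% to 71% counted from screening, and is 46% if counted from randomisation over a 13-week window. These shares rest on an assumed season length and uniform entry, and crossing a calendar boundary is not itself a measured drift.

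The defect is confined to between-visit tests and to changes after Week 4. It is most serious for the diary and the Raynaud's condition score, and less so for thermography, which ends at Week 8. The size and direction of any seasonal shift cannot be derived from the documents. The randomised contrast to Week 4 is unaffected.

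**What to change.** 1. In Potential pitfalls and contingency plan, replace *eliminate* with *limit*, and say that the rule reduces seasonal differences between subjects but not within them.
2. In Statistical analysis, state that efficacy conclusions rest only on the concurrent gammaCore-versus-sham contrasts at Week 0, at Week 4 and over the Week 0-4 diary.
3. In the same section, report between-visit changes and all open-label changes after Week 4, including Aim 3, as descriptive: estimates with confidence intervals and no significance claims.

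The cost is a few sentences. Arms, visits and sample size stay as they are. The real loss is that before-after comparisons no longer count as tests.

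Stating the intended season and recruitment window, recording visit dates and outdoor temperature, and randomising in small blocks are inexpensive options. They would help a reader judge the descriptive changes or keep the arms balanced over time, but the point does not depend on them, and blocking does nothing about drift within a subject.
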